4.3 Schedule of Procedures

Qualitative Study

Procedures	ECHO Intervention sessions 1-5 (Received as part of standard clinical practice*)	Review (Standard clinical practice 12 weeks after session 5)	Telephone call (At least 24 hours after review)	Interview (Within 12 months of session 5)**
Recruitment for Qualitative Study		X		
Telephone call to discuss participation queries			X	-
Interview			· ·	X

* Participants for the Qualitative Study do not need to participate in the ECHO Intervention Study

** Interviews will be conducted a minimum of 24 hours after Review session

ECHO Intervention Study

Department for Education

· · · · · · · · · · · · · · · · · · ·	ECHO Intervention Study visits (7)			
Procedures	Screening	Baseline (Minimum 24 hrs after screening)	ECHO Intervention sessions 1-5***	Review ^{****} (12 weeks after session 5)
Recruitment for ECHO Intervention Study	X		••••••••••••••••••••••••••••••••••••••	
Informed consent		Х		· ·
Demographics	· · · · ·	Х	· · · · · · · · · · · · · · · · · · ·	
All ECHO Intervention Study outcome measures collected		×		X
Parent-Child Interaction Pre/Post Measure completed		X	X	x

***May be conducted between 3 and 21 days after previous visit (including baseline visit)

****May be conducted up to 4 weeks before or after the 12-week window

4.3.1 Rationale for Schedule of Procedures

The structure of the ECHO Intervention schedule is based on the successful Early Years Communication and Language Pathway that has been embedded in Manchester since 2015 (Lee & Ashworth, 2020). Attendance from local families was more consistent when intervention was limited to 5-6 sessions offered weekly and delivered flexibility around family schedules.

Review at 3 months following the final intervention session is based on recommendations in the CSBS DP and WellComm Language Screen Toolkit manuals (Wetherby & Prizant, 2002; GL Assessments, 2015).

Interviews will be conducted within 12 months of the final intervention session to allow for recruitment during standard clinical visits to minimize disruption to families while allowing for the inclusion of families at different time periods following intervention. This will give a broader range of perspectives that may develop over the year postintervention. This schedule also allows flexibility in the scheduling of interviews, which may support the inclusion of a wider range of families.

2.

Department for Education

Study Sample and Recruitment

5.1 Eligibility Criteria

All individuals will be considered for inclusion in this study regardless of age, disability, gender reassignment, marriage and civil partnership, pregnancy and maternity, race, religion and belief, sex, and sexual orientation except where the study inclusion and exclusion criteria EXPLICITLY state otherwise.

5.1.1 Inclusion Criteria

Qualitative Study:

- Parent/caregiver received at least one ECHO Intervention session within the last 12 months.
- Parent/caregiver residing within the Manchester Local Authority at the time of interview.
- Parent/caregiver having a sufficient level of oral language skills in any language to participate in an in-depth interview as assessed by the researcher's judgement.

ECHO Intervention Study:

- Parent/caregiver of a child aged less than 24 months at the start of intervention.
- Parent/caregiver of a child who scored Red on the WellComm Language Screen within 3 months of the start of intervention.
- Parent/caregiver of child who scored High Likelihood of autism on Social Attention and Communication Surveillance (SACS-R) tool.
- Residing within the Manchester Local Authority for the duration of intervention.

5.1.2 Exclusion Criteria

Qualitative Study:

- Current significant and ongoing safeguarding concerns.
- Learning disabilities and/or communication difficulties or disorders that significantly impact parent/caregiver's capacity to give informed consent and participate in interview even with interpreter support and use of supportive communication strategies.

ECHO Intervention Study:

- Family currently receiving intervention from another Speech and Language Therapy Service.
- Parent/caregiver already taking part in the study with another child.
- Child or parent/caregiver has a diagnosis of visual, motor, or hearing impairment.
- Child has a diagnosis of a developmental disorder other than autism.
- Current significant and ongoing safeguarding concerns.

Date: 16.05.2024

5.2 Study Setting and Sample Identification

Parents/caregivers of children aged between 12 and 24 months with significant language and communication difficulties and significant social communication difficulties residing in the Manchester Local Authority area.

Due to the large multi-ethnic and multilingual population in Manchester, it is anticipated that the study population will include families from multi-ethnic backgrounds with English as an Additional Language. The intervention has been designed with cultural diversity in mind and interpreters will be provided for families as needed.

More families of low socio-economic status are likely to be eligible for the study based on prevalence data that children from more deprived backgrounds are at risk for significant communication difficulties.

This is a single-centre study only and recruitment will take place at the parent/caregiver's home, or another suitable location if preferred . Participants will be identified by Speech and Language Therapists in the Early Years Communication and Language Team who will identify suitable recruits at initial appointments. Suitable recruits will then be approached with a Participant Information Sheet.

5.3 Sampling

5.3.1 Size of Sample

Qualitative Study

Data collection in the form of semi-structured in-depth interviews will be conducted until saturation of themes in the data collected is reached. It is expected that between 8-12 families will need to be interviewed to achieve saturation, based on similar literature (Neely et al., 2015; Thompson et al., 2017). This is consistent with the approach outlined in Braun and Clarke (2019).

ECHO Intervention Study

It is expected that 40 families will be recruited. This is a pragmatic sample size for an early exploratory study designed to generate hypotheses. The decision to target 40 families is based on prior experience with the intervention and considerations of time constraints, deeming it a realistic goal for recruitment. Allowing for 10% dropout, a medium effect size of 0.48 can be detected with alpha of 0.05 and 80% power. Assuming a clinical difference of 7, this equates to a standard deviation of 14.6.

5.3.2 Sampling Technique

Participants will be selected using a convenience sampling technique from all eligible patients accessing the Early Years Communication and Language Pathway. This sampling technique is used as there is only a small population of participants who can be identified using available resources for this study. Convenience sampling is a more cost-effective method of sampling for a study of this scope (Jager et al., 2017). A convenience sampling technique will limit generalizability (Jager et al., 2017) and further research will be necessary if the study demonstrates effectiveness in this limited sample.

Manchester University NHS Foundation Trust

This study is not blinded as there is no comparison group. The intervention will be delivered by different staff to those collecting baseline and endpoint measures to reduce potential bias.

5.4 Recruitment

Qualitative Study

All eligible families who have previously completed the ECHO Intervention will be offered the opportunity to participate in this Qualitative Study. A Speech and Language Therapist in the research team will inform these families of their eligibility to take part in interviews about their experiences in the ECHO programme during routine appointments in clinical practice, and a Participant Information Sheet will be shared with the potential participant. Families will be contacted by telephone by an administrative assistant from the research team at least 24 hours after receiving the Participant Information Sheet to ask if they are interested in participating, unless they have previously indicated they are not interested in participating.

ECHO Intervention Study

All eligible families referred for ECHO Intervention as part of the local Early Years Communication and Language Pathway will be offered the opportunity to participate in the effectiveness study. Families will be informed of the study and given a Participant Information Sheet by a Speech and Language Therapist in the research team after the child has scored High Likelihood on SACS-R during standard clinical practice. Families will be booked for an initial session as part of standard clinical practice and will be asked by a Speech and Language Therapist in the research team if they would like to participate in the ECHO Intervention Study during this visit. If a family consents, they will be asked to sign a consent form and baseline measures will be taken. If a family does not consent, they will receive the ECHO Intervention as part of standard clinical practice, but data will not be included in the study.

Children will be referred to the Early Years Communication and Language Team by the Health Visiting Team following their 9-month Child Health Check offered to all families. Children may also be referred by Outreach Workers in the local children's centres following a WellComm Language Screen offered during Outreach support or whilst parents/caregiver_ attended the centre. Children referred to the Early Years Communication and Language Team will be screened for eligibility for the ECHO Intervention Study. These two referral pathways should increase the likelihood of low income and isolated families being referred as well as families reluctant to engage with medical services. Interpreters are available to referrers so that families with limited English skills may also receive support.

As part of standard practice, all children referred to the Early Years Communication and Language team who score Red on WellComm are offered screening with the Social Attention and Communication Surveillance Tool (SACS-R) unless:

- they have an identified visual or hearing difference,
- · they have identified motor differences other than delayed development,
- they have an identified developmental or medical condition that impacts social communication development, or
- there is concern that offering the SACS-R at this time may cause distress or harm.

Date: 16.05.2024

Manchester Local Care Organisation MANCHESTER CITY COUNCIL

Department for Education

Manchester University NHS Foundation Trust

As part of standard practice, children who score High Likelihood for autism on the SACS-R are referred for early communication intervention within the Early Years Communication and Language Service. Parents/caregivers of these children will be assessed by Speech and Language Therapists within the research team for their eligibility to participate in the ECHO effectiveness study. Speech and Language Therapists in the research team have access to patient details as part of standard clinical practice. A parent/caregiver's decision whether to participate in the study will not impact on the treatment options they will be offered or the treatment they will receive.

Parents/caregivers will be invited to participate in the study after their treatment options have been discussed at the initial appointment with the Early Years Communication and Language Team. A Speech and Language Therapist will give eligible parents/caregivers a Participant Information Sheet and will inform parents/caregivers that they will be asked about their willingness to participate at the next appointment. A home visit will be booked for 1-2 weeks' time.

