3.1 Objectives

Qualitative Study Objectives:

- i. Primary Objective: Inform intervention and its measurement development, implementation, and sustainability (Reflexive Analysis (Braun & Clarke, 2006; Braun & Clarke, 2020)).
- ii. Secondary Objectives:
- o Identify perceptions of the intervention
- Identify any benefits and/or harms potentially related to the ECHO Intervention not anticipated by clinicians
- o Identify barriers to implementation and embedding of strategies.

ECHO Intervention Study Objectives:

- i. Primary Objective: To assess whether the ECHO Intervention is effective at improving child communication.
- ii. Secondary Objectives: To test whether the ECHO Intervention is effective at:
 - o Improving parent/caregiver wellbeing and efficacy
 - Increasing parent/caregiver use of parent-child interaction strategies supporting communication development
 - Increasing child's language skills
 - Increasing child's social communication skills.

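### The Qualitative Study admits parents after one session, but its recruitment text and schedule give a route only to families who completed ECHO, so its findings on barriers and harms will come essentially from completers

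*Protocol*

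**What the plan says.** **Eligibility (Protocol 5.1.1, Qualitative Study).** The exposure criterion is "Parent/caregiver received at least one ECHO Intervention session within the last 12 months". Completing the programme is not required. Residence and language criteria also apply, as do the exclusions in 5.1.2.

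**Recruitment (5.4, same study).** The offer is worded: "All eligible families who have previously completed the ECHO Intervention will be offered the opportunity to participate in this Qualitative Study". These families hear about the interviews from a therapist "during routine appointments in clinical practice" and receive the information sheet. A telephone call follows at least 24 hours later.

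**Schedule (4.3, Qualitative Study).** The only recruitment mark is in the Review column, which is headed "Review (Standard clinical practice 12 weeks after session 5" (closing bracket omitted). The interview column is headed "Interview (Within 12 months of session 5" (likewise), and a footnote adds: "Interviews will be conducted a minimum of 24 hours after Review session". Another footnote says that interviewees need not be in the ECHO Intervention Study.

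**Rationale (4.3.1).** "Interviews will be conducted within 12 months of the final intervention session to allow for recruitment during standard clinical visits". The same paragraph hopes that flexible scheduling will bring in a wider range of families.

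**Purpose (3.1).** The secondary qualitative objectives are to identify perceptions, benefits or harms that clinicians did not anticipate, and barriers: "Identify barriers to implementation and embedding of strategies".

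**The concern.** The inclusion criterion and the recruitment route describe different groups. Families inside the first but outside the second are mainly those who began ECHO and stopped. They are plausibly well placed to describe what made the programme hard to take up, or any harm they met.

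The interviews have practical consequences. Section 9.1 uses them to decide how ECHO may need to change, section 6.1 uses them to choose themes for later outcome measures, and section 7.5 presents them as the systematic review of the programme. If nearly all the accounts come from families who stayed to the end, these decisions rest on a group selected for having found the programme workable. Nothing in the protocol would tell a reader of the results that this selection took place. Section 5.3.2 accepts limited generalisability from convenience sampling, but it does not mention a frame made up of completers.

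**Working it through.** The protocol states no figure on this point, so there is none to reproduce. The check sets the three sections side by side for each kind of family that has had at least one session in the last 12 months and meets the other criteria.

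| Family | 5.1.1 eligibility | 5.4 offer | 4.3 schedule |
|---|---|---|---|
| All five sessions, attended Review | Eligible | Offered | Recruited at Review |
| All five sessions, missed Review | Eligible | Within the completed group; could be told at another routine appointment | No recruitment point; no Review for the interview to follow |
| Stopped after sessions 1-4, still attended a Review | Eligible | Not in the group offered | Not provided for: Review and interview are both dated from a session 5 that did not happen |
| Stopped after sessions 1-4, no Review | Eligible | Not in the group offered | No recruitment point and no interview window |

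Only the first row passes all three sections. The second fails on the schedule alone. The third and fourth fail on both the offer and the schedule.

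**The 12-month clock.** It runs from session 5 in the 4.3 table, from the final intervention session in 4.3.1, and back to any session received in 5.1.1. For a completer the final session is session 5, so the table and 4.3.1 agree. For a family that stopped early, the 4.3 clock has no start date.

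**Size.** Let d be the share of families with at least one session who stop early, and n the number of interviews. Section 5.3.1 expects n = 8 to 12. If interviewees were drawn at random from everyone meeting 5.1.1, with equal uptake, the chance of at least one non-completer would be 1 - (1 - d)^n. The protocol gives no value for d, so every value below is an assumption.

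| d (assumed) | n = 8 | n = 12 |
|---|---|---|
| 5% | 1 - 0.95^8 = 34% | 1 - 0.95^12 = 46% |
| 10% | 1 - 0.90^8 = 57% | 1 - 0.90^12 = 72% |
| 20% | 1 - 0.80^8 = 83% | 1 - 0.80^12 = 93% |
| 30% | 1 - 0.70^8 = 94% | 1 - 0.70^12 = 99% |

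The answer runs from 34% to 99% depending on an unknown. The table shows why the loss cannot be sized from this document; it does not estimate it.

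**The case against.** **The text is looser than it looks.** Section 5.4 does not say that completers are the sole group and does not define completion. It refers to routine appointments in general, and 4.3.1 speaks of the final session, not session 5. A reader might infer that no early stopper could ever be invited and that none of the 8-12 interviews could come from one. The documents do not support that: a family that stopped early but still attended a Review might be approached in practice. What stands is that no section provides for this.

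**The 10% dropout figure.** A reader might apply the 10% in 5.3.1 and expect 0.8 to 1.2 non-completers among 8-12 interviews. That figure is the ECHO Intervention Study's sample-size allowance for a baseline-to-follow-up comparison. It is not a rate of stopping before session 5, and interviewees need not belong to that study.

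**Completers can report barriers and harms too.** This is true. Families who received all the strategies and had 12 weeks to use them may be the best source on embedding them. The tilt towards acceptability is a plausible inference, not something the protocol demonstrates.

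**Harms and reasons for stopping are recorded elsewhere.** Section 8 collects adverse events at each visit, including wellbeing and family circumstances, and section 5.5 provides a withdrawal form. Both serve study participants, whereas an interviewee may have had ECHO only as usual care. A participant may withdraw without giving a reason. Neither record replaces an account of perceptions or barriers.

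**Qualitative samples need not be representative.** Agreed, but 5.1.1 deliberately admits these families, so the recruitment route should be able to reach them.

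**Conclusion.** The point holds as an inconsistency between 5.1.1, 5.4 and 4.3 that affects who is interviewed. Staff cannot follow all three sections for a family that stopped before session 5, and the schedule also omits one that finished but missed the Review. Followed as written, the plan gives an essentially completer-only sample for objectives that include barriers and unanticipated harms.

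The conclusion rests on two readings: that the group named in 5.4 is the group to be invited, and that the single recruitment mark in 4.3 is the intended recruitment point. The direction of the tilt is a judgement, and its size is not known.

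The consequence is confined to the qualitative component; the CSBS DP comparison is untouched. The mismatch should be corrected because the protocol's own criterion already admits these families and the interviews will shape the programme.

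**What to change.** Reconcile 4.3, 5.1.1 and 5.4 as follows:

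- In 5.4, extend the invitation to all families meeting 5.1.1, naming those who stopped before session 5 and those who missed the Review.
- In the 4.3 table, add a recruitment point that does not depend on the Review. Limit the rule that the interview follows the Review to families who have one.
- Count the 12 months from the last session received, in the table and in the text.
- Where there is no appointment, post the information sheet. Then use the telephone call, interpreter support and postal consent already described in 5.5.
- Report how many interviewees did not complete ECHO.

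No fixed quota of non-completers is needed, because 5.3.1 samples to saturation and the early-stopping rate is unknown.

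The cost is a small protocol amendment handled under 7.3.1, some posted sheets and a few extra calls, with the number of interviews unchanged. Uptake among families who stopped will probably be low, so the sample may still be mostly completers; the reported count would show this.

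If the team prefers not to widen recruitment, the consistent alternative is to restrict 5.1.1 to completers, settle in 4.3 whether a completer who missed the Review can be interviewed, and state that the findings on barriers and harms apply to completers only.

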5.5 Consent

Qualitative Study

Participants will be contacted by a member of the research team via telephone at least 24 hours after receiving a Participant Information Sheet to discuss their interest in participation. Information in the Participant Information Sheet will be reviewed verbally during this discussion to ensure it has been read and understood. Telephone interpreting services will be used if requested by families with English as an additional language.

If a family gives verbal consent to participate during the telephone conversation, a consent form will be sent to the participant by post with a pre-paid, self-addressed envelope for participants to return consent forms by post. Participants will be contacted to book an interview once the written consent form has been received by the Early Years Communication and Language Team.

All research team members obtaining consent will have completed training in obtaining informed consent. Participants will be given an opportunity to ask questions during this discussion.

ECHO Intervention Study

Eligibility and discussion of the purpose of the ECHO Intervention Study will occur at the initial contact visit with a Speech and Language Therapist from the research team. A Participant Information Sheet will be given to families and a baseline visit will be booked for at least 24 hours later. A baseline visit is part of standard clinical care for the ECHO Intervention and can be completed on the same day as the first intervention session. At the baseline visit, the Speech and Language Therapist will discuss participation in the study with parents/caregivers. If parents/caregivers consent, the consent form will be completed with the Speech and Language Therapist. Consent forms will be held securely on MFT property in the Early Years Communication and Language Team Office. Where appropriate, interpreters will be present to support parents/caregivers to understand information relevant to the intervention study and informed consent.

All parents/caregivers will be asked if they continue to consent to participation at each intervention session carried out in the home, or another suitable location if preferred, with a

Date: 16.05.2024

Language Development Worker meeting ECHO training requirements detailed in the ECHO Manual.

Withdrawals can either be made by the participant or the research team. Participants may withdraw from the study at any time, without giving a reason. The research team may withdraw a participant from the study for welfare or safeguarding reasons, if participation is no longer in their interest, or if contact for follow-up is lost for a prolonged period of time. The research team will complete a withdrawal form stating the date and reason for withdrawal. Data collected up until the point of withdrawal will be used unless participants request their data to be removed from the study. If participants request all data to be removed, this information will be deleted. Participants will not be replaced.

